4.3 Number of subjects required

We estimate a completed sample size at follow up of 284 children. Allowing for an attrition rate of around 30% we will need to recruit a total of 406 children to the trial to achieve the estimated sample of 284 (who will complete the trial). Within the study hospitals some 1700 tonsillectomies/adeno-tonsillectomies are currently performed annually. Only two thirds of these will have recurrent sore throats. In any trial where the intervention is widely used in current practice there are likely to be large numbers of eligible participants who opt for the intervention treatment and decline participation in the trial. We estimate that this could be up to one half of all eligible referrals from primary care. The maximum available for randomisation is therefore estimated as 566 per annum. Loss of eligible subjects in the trial is expected due to holiday periods and 'winter pressures'. On the experience of loss in other trials (50%) a conservative estimate would be 283 per annum. If we assume a conservative rate of attrition of 30% over two years we would expect 198 completing trial participants to be recruited in a 12 month period. Given seasonal effects a full 2 years would be necessary to recruit the estimated sample size.

The cohort sample will be identified from participants who indicated a preference not to be randomised within the trial and who agreed to data collection. An appropriate sampling fraction will be used once non-participation in the trial can be estimated.

5 Subject recruitment

Recruitment to the study will take place in secondary care. All GP referrals to study centres of children with recurrent sore throat will be considered by participating surgeons. Arrangements are in place in each centre for eligible children to be referred to the clinical applicants. GPs will be informed of this reorganisation. This will facilitate efficient use of outpatients clinics at which trial participants would be recruited.

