6.2 Control

Non-surgical conventional medical treatment only will be used. There will be no active intervention protocol since no single prescribing strategy would be able to cover all patients³⁴. The referring GP will be free to treat as in their current practice. The use of usual treatment rather than an active intervention protocol is considered important for the implementation of study findings since 'surgical enthusiasts' may argue against the findings were the control group to be atypically and over rigorously treated

7 Randomisation

Independent world wide web based computer randomisation will allocate participants to treatment arms. Randomisation will take place once informed consent to the study has been completed and base-line data collected. The sample will be stratified by age of child at last birthday. Blocked randomisation will be used to ensure that within each centre, within each of the three age groups (4-7, 8-11, 12-15) children will be allocated in equal numbers to each arm of the trial. Where trial sites are unable to access the world wide web they will telephone the coordinating centre (University of Newcastle) in order for web based randomisation to be completed on their behalf.

Sampling for the cohort study will similarly be stratified by age.

8 Blinding

Health technology assessment is essentially a pragmatic activity conducted in normal clinical practice, rather than an exploratory activity conducted in highly controlled settings. It follows that blinding doctors and patients to treatment is not desirable since it distorts normal clinical practice. Nor is it practicable. In contrast, blinding assessors is important because it minimises subjective bias towards a given treatment. All research staff conducting interviews or processing postal questionnaires and diaries will be blind to treatment modalities of all participants. This will be facilitated by separating the responsibility for recruitment and randomisation from outcome assessment. Furthermore, participants will be encouraged to respond to questions without describing their treatment regime. In this way, we will minimise subjective bias towards a given treatment.

9 Data

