9.1 Data to be collected

All participants will be followed-up for 24 months from the date of initial randomisation. To minimise recall bias, data on sore throats will be gathered by a simple, structured daily health diary completed and returned by participants on a monthly basis for 24 months. Experience of similar studies suggests that with appropriate telephone reminders 90% of diaries will be returned completed.

In addition simple outcome questionnaires will be administered to trial and cohort study participants. Overall we anticipate an 80% response rate. Interview surveys will be done at 3, 12 and 24 months after randomisation. A baseline questionnaire will be completed by all participants upon recruitment to the trial. The greater frequency of data collection in the first 12 months is necessary in order to capture data on expected changes in direct and social costs to participants in the first 12 months. Experience also suggests that data on consultation rates and prescribed medication can be gathered most accurately and reliably from medical records. Manual abstraction will be performed by trained research nurses at the end of follow up for all participants

| Primary clinical outcome | Measurement method | When | Where |
|---|---|---|---|
| Number of events of recurrent sore throat | Self-completed diary (by parent or child) | Daily recording but collected four-weekly for 24 months | Participants' homes |
| Secondary clinical outcomes | Measurement method | When | Where |
| Number of events of recurrent sore throat, otitis media or URTI recorded by GPs | GP records | End of 24 month follow-up period | General practices (GP records) |
| Adverse events: re-referral for tonsillectomy; number of symptom-free days | Self-completed diary (by parent or child) and GP records | Daily recording but collected four-weekly for 24 months and end of 24 month follow-up period | Participants' homes (diary) and general practices (GP records) |

Table 1 Clinical outcome measures for trial and cohort studies

Table 2 Measuring treatment impact

| Impact | Measure | When | Where |
|---|--|-------------------------------------|--------------------|
| Costs to participants of the condition and its management | Questionnaire to children and parents | Base-line, 3, 12 and 24 months | Participant's home |
| Social costs: e.g. time off school and parental time off work | Self-completed diary (by parent or child) | Base-line, 3, 12 and 24 months | Participant's home |

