10.1 Sample size calculation

In this trial we anticipate a fairly large difference in the primary clinical outcome (the reported number of episodes of sore throat in the two years after randomisation) with an effect size of around 1.0, but a smaller difference in a number of psycho-social outcomes including health-

related quality of life, with an effect size of 0.33. No standard sample size formula is available for economic evaluations, and a number of methods have been proposed ⁴⁸⁻⁵⁰. The information which is currently available limit the use of such methods in practical applications. Published data¹⁸ suggest that tonsillectomy may lead to a reduction of approximately 1.5 days per year in missed schooling. Given a reported standard deviation of 4.5, to detect this difference with 80% power we would need approximately 142 children in each arm of the trial assuming a significance level of 5%. A sample size of 142 children in the cohort group will allow us to detect similar differences between the cohort group and propositi.

The sample will be stratified by age. With a total of 284 children, we will have approximately 47 randomised to each treatment arm in each strata. Given that the standard deviation of the number of sore throats per year is estimated at approximately 2.0¹⁸, we will be able to estimate the difference between treatments in each strata with a standard error of 0.41. (Equivalently we would have 90% power to detect a difference of 1.35 episodes of sore throat per year in each strata assuming a type 1 error of 0.05).

It is anticipated that the difference in outcome between the two arms of the trial will be approximately 2 episodes in the second year of follow up. A sample size of 142 children in each arm should enable us to measure this difference with sufficient precision to undertake a meaningful economic analysis.

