10.2 Statistical analysis

10.2.1 Main analysis

An intention to treat analysis will be performed. In particular, children randomised to nonsurgical conventional medical treatment will be retained in that group for the analysis even if they subsequently receive a tonsillectomy.

The primary clinical outcome measure will be the number of episodes of sore throat. This variable will be analysed using generalised linear modelling assuming a Poisson error structure with a log link function⁵¹. By fitting the difference between the two experimental groups as a fixed effect, interval estimates of the effect of tonsillectomy (in each of the first two years of follow up) will be generated. These estimates will then be used in the economic analysis.

The same approach will be used to analyse the other outcomes. A Poisson error structure will be assumed for data in the form or a count (such as the number of episodes of absence from school) and normal error structure adopted for continuous variables (such as the quality of life indices).

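### The sample size rests on days of missed schooling per year, but the only absence variable named for analysis is Poisson-modelled episodes, and Table 2's schedule does not fit a daily diary

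*Protocol*

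**What the plan says.** Section 10.1 (Sample size calculation) bases the trial's size on school days lost. It reports published data that "tonsillectomy may lead to a reduction of approximately 1.5 days per year in missed schooling", and continues: "Given a reported standard deviation of 4.5", to detect this with "80% power we would need approximately 142 children in each arm of the trial assuming a significance level of 5" per cent. Section 4.3 carries the resulting 284 completers to the recruitment target: "Allowing for an attrition rate of around 30% we will need to recruit a total of 406 children". The cohort of 142 is justified in section 10.1 by the same size of difference. The same section expects an effect size of about 1.0 for the primary outcome, and smaller differences in psycho-social outcomes, including quality of life, "with an effect size of 0.33".

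Section 10.2.1 (Main analysis) extends the modelling approach to the other outcomes: Poisson errors for counts, normal errors for continuous variables such as quality of life. Its example of a count is "such as the number of episodes of absence from school". Days of missed schooling are not mentioned there.

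Table 2 in section 9.1 has the row "Social costs: e.g. time off school and parental time off work", measured by self-completed diary at baseline, 3, 12 and 24 months. Table 1 in the same section describes the self-completed diary as filled in daily and collected every four weeks for 24 months. Section 9.1.1.3 monitors time off school for the economic evaluation.

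**The concern.** Three parts of the protocol describe school absence differently. Section 10.1 uses days per year compared as means, section 10.2.1 uses episodes with a Poisson variance, and Table 2 gives four collection points for an instrument that is elsewhere continuous. An episode can last one day or many, so the number of episodes is not a rescaling of the number of days. The power calculated for one does not transfer to the other.

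The sample size of the randomised trial and of the cohort depends on this quantity. A reader of the results would expect the absence comparison to be the one with the stated 80% power; under section 10.2.1 as written, it need not be. There is also a variance question. If the absence variable became days and were still treated as a count, the Poisson rule would conflict with the SD used for sizing. Precision would be overstated for a quantity that also enters the economic evaluation, where section 9.1.1.3 makes a statistically significant difference one of two routes to a resource being costed.

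**Working it through.** **Inputs.** Difference 1.5 days per year, SD 4.5, power 80%, significance level 5%, 142 per arm, effect sizes 0.33 and about 1.0 (all section 10.1); equal allocation (section 7: "children will be allocated in equal numbers to each arm of the trial"); attrition 30% (section 4.3). Sidedness is not stated; two-sided reproduces the figure, while one-sided would give 112 per arm.

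**1. The plan's own figure.** n per arm = 2 × [SD × (1.960 + 0.842) / difference]² = 2 × [4.5 × 2.802 / 1.5]² = 141.3, rounded up to 142. Power at 142 is 80.2% (79.9% with the noncentral t). Recruitment: 284 / 0.70 = 405.7, so 406. Both figures are correct for a comparison of mean days.

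**2. Which planned analysis has this power.** The standardised difference is 1.5 / 4.5 = 0.333, which matches the 0.33 stated for psycho-social outcomes. With 142 per arm, power = Φ(d × √(142/2) − 1.960):
- d = 0.333: Φ(2.809 − 1.960) = 80.2%
- d = 0.33: Φ(2.781 − 1.960) = 79.4%

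So the normal-error analysis of quality of life has about 79–80% power at the stated effect size. For the primary outcome at effect size 1.0, power exceeds 99.9% (16 per arm would give 80%).

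**3. Episodes of absence.** The protocol gives no mean, SD or expected difference for episodes, so no power can be derived from it. To illustrate the spread, assume an absence lasts 2 to 3 days, so that 1.5 days correspond to 0.75 to 0.5 episodes a year, and assume an SD of 1.0 to 2.5 episodes. The standard error is SD × √(2/142) = SD × 0.1187.
- Worst corner: 0.5 / (2.5 × 0.1187) = 1.685; power Φ(1.685 − 1.960) = 39%.
- Best corner: 0.75 / (1.0 × 0.1187) = 6.32; power over 99%.

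These are assumptions. They show only that the 80% cannot be read across.

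**4. Days under the Poisson rule.** A Poisson variance equals the mean. The stated SD gives a variance of 4.5² = 20.25, so the two agree only at a mean of about 20 days a year. At a lower mean, the ratio of the model standard error to the true one is √mean / 4.5, and the ratio is the same on the log scale:
- mean 4 (assumed): 2.00 / 4.5 = 0.44
- mean 10 (assumed): 3.16 / 4.5 = 0.70

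The protocol states no mean for days of missed schooling.

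**5. Collection.** Table 2 names the self-completed diary as the source for time off school but gives the same four time points as its questionnaire rows. Table 1 gives the self-completed diary a continuous 24-month schedule. The text of section 9.1 describes the daily diary as gathering sore-throat data and does not say whether it also records absence. From these passages one cannot tell whether absence is recorded every day, recalled at four visits, or extracted from selected diaries.

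**The case against.** The strongest reply is that a matching analysis is planned. Section 10.1 turns to missed schooling straight after discussing sample size for economic evaluations. Section 9.1.1.3 monitors time off school, and section 10.2.3 plans to compare use of resources and costs on arithmetic means by t-test or bootstrap. That could cover a difference in mean days. Quality of life has the same standardised difference and a normal-error analysis. Episodes of absence are only an example, and the approach covers the other outcomes in general.

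Much of this stands, and it rules out some stronger readings:

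- A reader might infer that the 80% applies to no planned analysis. The documents do not support that: it holds for quality of life, and a comparison of mean time off school could fall under section 10.2.3.
- A reader might infer that days per year cannot be obtained, or that only a few weeks of follow-up would be covered. Table 2 names the diary, no sampling window is stated, and the diary form is not shown. The tables conflict; that does not prove the data are missing.
- A reader might turn step 4 into an inflated false-positive rate (17–38% at the assumed means). That needs means the protocol does not give, and days fitted as plain Poisson, which it does not say will be done.
- A reader might call missed schooling an omitted outcome. Section 3.4 lists clinical outcomes and adds that costs and quality of life will be assessed; time off school is placed in Table 2 as an impact measure.

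What the reply does not remove is that section 10.1 says days, section 10.2.1 says episodes, and Tables 1 and 2 disagree about the diary. No passage links the sizing variable to a defined analysis. An analysis plan can settle the model, but it cannot supply absence data that were not collected.

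**Conclusion.** The point holds as an inconsistency in the quantity that fixes the trial's size. The arithmetic behind 142, 284 and 406 is right for mean days of missed schooling per year. That power does not carry over to episodes of absence, the only absence variable named in section 10.2.1, and power for episodes cannot be computed from the document. It does hold at about 79–80% for quality of life at 0.33.

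The variance problem is conditional. It arises only if days are analysed under the Poisson rule for counts, and its size (standard errors 44–70% of the true ones) rests on assumed means of 4 to 10 days. The firm part is that the protocol's own SD is compatible with a Poisson variance only near 20 days a year. The primary outcome is not affected, so this should be corrected but does not threaten the trial's main conclusion.

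**What to change.** 1. Reconcile Table 2 with the existing diary in Table 1, so that days off school are counted from the four-weekly diaries over the 24 months.
2. In section 10.2.1, replace episodes of absence with days of missed schooling per year, analysed as a difference in mean days with a variance that allows for the stated SD (robust standard errors or an overdispersed model such as the negative binomial).
3. In section 10.1, state that the 80% power refers to that analysis and, at an effect size of 0.33, to quality of life.

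If the diary already records absence, the cost is wording plus a small amount of data entry and analysis. If it does not, follow-up already completed cannot be recovered: this version is dated November 2007 and the study is due to end in July 2008. The protocol should then state what absence data exist and tie the 80% to quality of life alone. Neither course changes the sample size or the primary analysis.

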10.2.2 Secondary analysis

The aim of secondary analysis is to determine whether we can identify groups of children who benefit from surgical treatment. It is hypothesised that disease severity may be an important factor. A severity index based on history of the condition during the year before entry to the study will be derived using data recorded in GP records. The relationship between severity and the effect of tonsillectomy will then be investigated using the modelling approach described above.

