A straw poll, for this protocol, of consultant otolaryngologists asked: what level of reduction in sore throat would justify removal of the tonsils? Replies were remarkably consistent - at least 2 sore throats fewer per annum. No published trial to date shows a benefit of this magnitude, even in the first year after surgery. There is a pressing need for a UK, pragmatic trial to evaluate the cost-effectiveness of childhood tonsillectomy.

2 Objectives and purpose

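### Section 10.2.2 relates severity to the effect of surgery through a log-link model but does not ask for the answer in episodes avoided per year, the scale on which the protocol describes benefit

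*Protocol*

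**What the plan says.** Section 10.2.1 sets the model for the episode count: "This variable will be analysed using generalised linear modelling assuming a Poisson error structure with a log link function". The group difference is fitted as a fixed effect, and interval estimates for each of the two years go forward to the economic analysis.

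Section 10.2.2 then gives its purpose: "The aim of secondary analysis is to determine whether we can identify groups of children who benefit from surgical treatment". It hypothesises that severity matters, derives an index from GP records for the year before entry, and closes: "The relationship between severity and the effect of tonsillectomy will then be investigated using the modelling approach described above". It names no scale, no interaction test and no decision rule.

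Where the protocol puts figures on sore-throat benefit, they are counts of episodes:
- Section 1.3 reports earlier trials as fewer episodes per year. It also cites a straw poll of consultants on what would justify surgery: "at least 2 sore throats fewer per annum".
- Section 9.1.1.2 measures cost-effectiveness benefit by the number of sore-throat events (and symptom-free days).
- Section 10.1 expects that "the difference in outcome between the two arms of the trial will be approximately 2 episodes in the second year of follow up", and states the precision within age strata as "90% power to detect a difference of 1.35 episodes of sore throat per year in each strata assuming a type 1 error of 0.05".

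**The concern.** Under a log link, the coefficient that links severity to the effect of surgery is the log of a ratio of rate ratios. It is zero when surgery removes the same proportion of episodes at every severity. If severe children have more episodes without surgery, the same proportion means more episodes avoided. Conversely, if every child avoids the same number, the proportion falls as severity rises and the coefficient is not zero. When control rates differ and surgery works, a constant ratio and a constant difference cannot both hold.

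The purpose of 10.2.2 is to find which children benefit. If the answer were read from the log-scale term alone, two wrong conclusions about episodes avoided become possible: that severity does not matter when severe children are spared more, or that milder children gain more when all gain equally. Either would bear on whom to offer surgery.

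**Working it through.** **The protocol's own figures.** No figure is given for the severity analysis. The related figures in section 10.1 reproduce. With SD 2.0 and 47 per arm per stratum, SE = 2.0 × √(2/47) = 0.413 (stated 0.41). For a difference of 1.35, 1.35/0.413 = 3.27, and power = Φ(3.27 − 1.96) = Φ(1.31) ≈ 0.905 (stated 90%). A difference of 1.5 days with SD 4.5, 80% power and 5% significance gives 142 per arm.

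**Algebra.** Let control rates be c₁ < c₂ and surgery rates s₁, s₂.
- Log-scale term: L = ln(s₂/c₂) − ln(s₁/c₁).
- Absolute term: D = (c₂ − s₂) − (c₁ − s₁).
- Constant ratio r < 1: L = 0 and D = (1 − r)(c₂ − c₁) > 0.
- Constant difference d > 0: D = 0 and L = ln(1 − d/c₂) − ln(1 − d/c₁) > 0, which reads as a weaker effect in severe children.

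**Hand check.** Assume two severity halves, 71 children per arm per half, one year of Poisson counts. Then SE(L) = √(Σ(1/rate)/71) and SE(D) = √(Σ rate/71), summed over the four cells. The rates are assumptions.
- Constant ratio, 2→1 and 4→2: L = 0, so rejection is 5%. D = 1.0, SE(D) = √(9/71) = 0.356, z = 2.81, power ≈ 80% (simulated 80%).
- Constant difference, 3→1.65 and 5→3.65: D = 0, so rejection is 5%. L = ln 0.73 − ln 0.55 = 0.283, SE(L) = √(1.413/71) = 0.141, z = 2.01, power ≈ 52% (simulated 53%).
- Opposite signs, 3→1.2 and 6→3.6: severe children avoid 2.4 episodes and milder children 1.8. L = ln(0.60/0.40) = 0.405, SE(L) = √(1.611/71) = 0.151, z = 2.69, power ≈ 77% (simulated 78%). The log-scale term points to less benefit in the severe half.

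**Dependence on the gradient.** This simulation uses 142 per arm, a severity score in equal thirds, gamma-Poisson counts with dispersion 0.1, and robust standard errors so that only the scale differs. The control SD is √[mean(μ + 0.1μ²) + var(μ)]. For 2/3/4 this is √(3.967 + 0.667) = 2.15, for 2.5/3/3.5 it is √(3.917 + 0.167) = 2.02, and for 2.7/3/3.3 it is √(3.906 + 0.060) = 1.99. The protocol's figure is about 2.0.

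| Assumed control rates per year | Ratio 0.5: log term | Ratio 0.5: absolute term | Difference 1.0: log term | Difference 1.0: absolute term |
|---|---|---|---|---|
| 2.7/3/3.3 | about 5% | 8% | 8% | about 5% |
| 2.5/3/3.5 | 5% | 16% | 14% | 5% |
| 2/3/4 | 6% | 53% | 43% | 6% |

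Repeat runs gave 53–57% and 40–43% for the two large entries in the last row; the other entries moved by a point or two. Steeper gradients or larger effects widen the gap:
- Rates 2/3.5/5, dispersion 0 to 0.2, ratio 0.5: 5–6% on the log scale against 69–89% on the absolute scale.
- The same rates, constant difference 1.0: 44–62% against about 5%.
- Rates 2/3/4, constant difference 1.5: 91% on the log scale. This implies rate ratios from 0.5/2 = 0.25 to 2.5/4 = 0.625.

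**The case against.** The strongest reply is that the faulted test is not in the text. Section 10.2.2 names no interaction test, null hypothesis or scale, and section 10.2.1 speaks of interval estimates. A log-link model yields fitted rates by arm and severity, from which episodes avoided follow directly. The analysis goes wrong only if a single log-scale p-value is reported. Much of this stands. A reader might infer that the protocol commits to that p-value, or that the log link is itself a mistake, and the text supports neither. Relative effect modification is a legitimate quantity. What remains is that the section fixes the model and link for this question and does not ask for the output that answers it in episodes.

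A reader might also treat the straw-poll figure as the yardstick for this analysis. Section 1.3 reports it as surgeons' opinion and section 10.2.2 does not adopt it. Nor do the documents show that the economic analysis would be misdirected: it measures benefit in events, and the rates can be converted.

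The size is fairly challenged too. The severity rates are assumed. The entry criteria in section 4.2.1 narrow the range, section 1.1 warns that impressive histories are often not confirmed, and an index from GP records will sort children imperfectly. The flatter gradients fit the protocol's SD slightly better, and there the contrast is small. Even at 2/3/4 the absolute-scale test misses the effect in nearly half of trials.

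Finally, an unseen SAP may settle the reporting scale. That is a reason to treat this as an improvement, not an error.

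**Conclusion.** The concern holds as a mismatch between the model assigned to the severity question and the scale on which the protocol describes benefit. The direction follows from the link function and needs no simulation. The size is conditional: modest if control rates barely rise with severity (about 5% against 8%, and 8% against about 5%, at 2.7/3/3.3), and material if they double from the mildest to the most severe third (about 5–6% against 53%, and 43% against 6%, at 2/3/4). These figures rest on assumed rates, equal thirds, 142 completers per arm, dispersion of 0.1 and a severity index that sorts children without error. They also take a treatment-by-severity term as the natural reading of 10.2.2. This is a worthwhile, inexpensive improvement to a secondary analysis and leaves the primary comparison untouched.

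**What to change.** Keep the log-link model. Add to section 10.2.2 that the severity relationship will be estimated as the surgery-minus-control difference in episodes per year across the severity index, with confidence intervals. Two routes serve: model-standardised rates with delta-method or bootstrap intervals, or an identity-scale interaction with robust standard errors. Report the log-scale interaction alongside as relative effect modification, and state that it will not be the sole basis for saying that severity does or does not matter. The straw-poll level in section 1.3 may be shown as context but not as a criterion. Because power for any interaction is limited here, the estimates and intervals should carry the interpretation.

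The cost is one or two sentences and a few lines of code, with no new data and no change in sample size. The downside is two scales to report and wider absolute-scale intervals in the most severe children.
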